9.4 Statistical Methods

Primary Objective

1. The primary intent-to-treat analysis will estimate progression free survival from initiation of definitive therapy by the Kaplan-Meier method. Median PFS and 95% CI will be determined. A total of 41 patients will be enrolled on the study.
2. A secondary proof of principle analysis will determine the clinical benefit of adding consolidation Pembrolizumab after definitive therapy. Only patients who receive consolidation Pembrolizumab are included in this analysis. It is expected that up to 15% of enrolled patients will have progressive disease or lingering toxicity and will not start Pembrolizumab after definitive therapy. Thus we anticipate that at least 35 patients will be included.

In this proof of principle analysis, we will compare progression free survival from initiation of definitive therapy to a historical control value. We assume the median PFS for the historical control population treated with standard therapy only is 6 months and the median PFS for the patients treated with definitive therapy and consolidation Pembrolizumab is 10 months. Assuming 35 patients are enrolled over 2 years and followed for an additional 3 months, the final analysis will have 80% power to detect an improvement in median PFS assuming exponential survival and 1-sided 5% significance level.

Secondary Objectives

1. Overall survival will be estimated by the Kaplan-Meier method. Median OS and 95% CI will be determined.
2. Toxicities will be graded, categorized and tabled. For the definitive therapy phase, we will report on adverse events which are grade 3 or higher treatment-related toxicities or any grade of pneumonitis or esophagitis. For the Pembrolizumab phase, we will report all treatment-related toxicities.

Exploratory Objective

1. Biomarkers will be tested for association with PFS using log rank test for categorical biomarkers and Cox proportional hazards regression for continuous biomarkers. Biomarkers will be tested for association with graded toxicity (i.e., worse toxicity grade) for specific categories of toxicity using chi square test for categorical biomarkers and Spearman's correlation for continuous biomarkers.

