8.1.2.6 Tumor Imaging and Assessment of Disease

The initial tumor imaging will be performed within 42 days prior to the first day of proton reirradiation or as indicated according to standard of care. Scans performed as part of routine clinical management are acceptable for use as the screening scan if they are of diagnostic quality and performed within 30 days prior to the first day of treatment. Tumor imaging will be repeated at the conclusion of chemoradiation and within approximately 30 days prior to the first dose of pembrolizumab. Imaging while on pembrolizumab will be performed every 12 weeks (1 day before Pembrolizumab up until the day of the next infusion) after the first dose of pembrolizumab or more frequently if clinically indicated. Tumor imaging timing should follow calendar days and should not be adjusted for delays in cycle starts or extension of Pembrolizumab cycle frequencies. This image schedule will also be adjusted per subject's insurance coverage.

For patients that receive at least one dose of Pembrolizumab, after the first documentation of progression (if the subject is clinically stable) confirmatory scans may be performed as early as 28 days later; alternately, the scan performed at the next scheduled time point (e.g. every 84 ± 7 days) may be used as confirmation.

After the first documentation of progression, it is at the discretion of the investigator either to verify true PD, to keep a clinically stable subject on trial treatment or to stop trial treatment until repeat imaging performed at least 28 days later confirms progression. Clinical Stability is defined as:

- 1) Absence of symptoms and signs indicating clinical significant progression of disease (including worsening of laboratory values) indicating disease progression.
- 2) No decline in ECOG performance status.
- 3) Absence of rapid progression of disease or progressive tumor at critical anatomical sites (e.g., cord compression) requiring urgent alternative medical intervention.

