8.1.5.3 Pre-Pembrolizumab Screening

Visit requirements are outlined in Section 7.0 - Trial Flow Chart.

Subjects will be eligible to move on to pembrolizumab treatment cycles if they received at least 50 Gy of reirradiation, if they have no progressive disease on tumor imaging, and if they do not have symptomatic CTCAEv5 grade ≥ 3 pneumonitis.

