9.3 Hypothesis/Evaluation

This phase II study evaluates a multi-stage treatment plan for recurrent disease that is comprised of definitive therapy consisting of proton reirradiation with or without chemotherapy, followed by consolidation Pembrolizumab, for recurrent NSCLC. A total of 41 patients will be enrolled on the study. Between the end of definitive therapy and the start of Pembrolizumab, there is a 4-12 week rest period. The primary intent-to-treat analysis will estimate PFS from start of definitive therapy, regardless of whether consolidation Pembrolizumab was administered. A secondary proof of principle analysis will estimate PFS in the subgroup of patients who receive definitive therapy followed by consolidation Pembrolizumab. The benefit of adding Pembrolizumab after definitive therapy will be determined in this analysis, by testing whether PFS is improved as compared to a historical control population who received standard therapy only. For this proof of principle analysis, the null hypothesis is that the median PFS from start of therapy for a recurrence of NSCLC is 6 months as compared to the alternative hypothesis that the median PFS is increased to 10 months.

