9.3.1 Analysis Endpoints

Primary

Progression Free Survival (PFS) per RECIST 1.1

Progression Free Survival is defined as the time from initiation of definitive therapy to the first documented disease progression per RECIST 1.1 based on radiologists' review or death due to any cause, whichever occurs first, or last patient follow-up that documented lack of disease progression. Patients who have not had disease progression or who have died, will be censored on the most recent clinical evaluation date that documented that they were progression-free.

Secondary

Overall Survival

Overall Survival (OS) is defined as the time from initiation of definitive therapy to death due to any cause or last patient contact alive. Subjects without documented death at the time of the final analysis will be censored at the date of the last follow-up.

Toxicity Determination

Tolerability of therapy will be determined on the basis of CTCAE adverse event reporting. Toxicity will be reported separately for definitive therapy and Pembrolizumab. For the definitive therapy phase, we will report on adverse events which are grade 3 or higher treatment-related toxicities or any grade of pneumonitis or esophagitis. For the Pembrolizumab phase, we will report all treatment-related toxicities.

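### Section 9's only powered efficacy test keeps pembrolizumab starters, who must first show no progression on imaging, yet counts their PFS from day 1 of reirradiation against a 6-month median with no matching selection described

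*Combined protocol and SAP*

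**What the plan says.** **Endpoint and time zero.** Section 9.3.1: "Progression Free Survival is defined as the time from initiation of definitive therapy to the first documented disease progression", or death.

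**Hypothesis.** Section 9.3, for the proof-of-principle analysis: "the null hypothesis is that the median PFS from start of therapy for a recurrence of NSCLC is 6 months", against an alternative of 10 months. The comparator is a historical population given standard therapy only. The same section adds: "The benefit of adding Pembrolizumab after definitive therapy will be determined in this analysis".

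**The comparison.** Section 9.4: "In this proof of principle analysis, we will compare progression free survival from initiation of definitive therapy to a historical control value".

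**Who is tested.** Section 9.4: "Only patients who receive consolidation Pembrolizumab are included in this analysis". It expects that "up to 15% of enrolled patients will have progressive disease or lingering toxicity and will not start Pembrolizumab after definitive therapy", and so plans on at least 35 of the 41 enrolled. It assumes exponential survival and a one-sided 5% level, and states 80% power.

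**The gate.** Section 8.1.5.3 lets patients go on to pembrolizumab only "if they have no progressive disease on tumor imaging", alongside conditions on radiation received and pneumonitis. Section 8.1.2.6 times the scan: "Tumor imaging will be repeated at the conclusion of chemoradiation and within approximately 30 days prior to the first dose of pembrolizumab". Section 3.1 gives 3-8 weeks of reirradiation, then 4-12 weeks before first dose.

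**Primary analysis.** The ITT analysis of all 41 patients gives a Kaplan-Meier median and 95% CI, with no test in Section 9.

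**The concern.** The tested patients are chosen by something that happens after time zero: reaching a later scan without progression. Their event-free weeks before first dose still count as PFS. The 6-month reference runs from start of therapy, and nothing says that those patients also had to be progression-free at a later point. This is immortal-time bias, and it runs in one direction, towards benefit. The plan foresees losses to progression but uses them only to reduce the number analysed from 41 to 35.

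This is the analysis in which 9.3 says the benefit of adding pembrolizumab will be settled. It could come out positive through selection alone.

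**Working it through.** **1. Inputs.** Null median 6 months, so hazard L0 = ln 2/6 = 0.1155 per month; alternative 10 months, L1 = ln 2/10 = 0.0693; 35 patients; 24 months' accrual plus 3 months' follow-up; one-sided 5% (9.3, 9.4). Uniform accrual is assumed.

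**2. The plan's 80%.** P(event) = 1 - [exp(-3L) - exp(-27L)]/(24L).
- Null: 1 - (0.7071 - 0.0442)/2.7726 = 0.761; x 35 = 26.6 events.
- Alternative: 1 - (0.8123 - 0.1539)/1.6636 = 0.604; x 35 = 21.1 events.
- Log-hazard power: z = [ln(10/6) - 1.645/sqrt(26.6)] x sqrt(21.1) = 0.88, or 81%. A cube-root version gives 79.5%; a simulated one-sample log-rank gives 78%.

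The stated 80% is reproduced, but only with the 10-month hazard acting from day 1 and no selection.

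**3. Where the gate falls.** First dose comes 3 + 4 = 7 to 8 + 12 = 20 weeks after day 1, and the gate scan up to about 30 days earlier.

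**4. Direction, without assuming a curve shape.** Suppose no drug effect and a true 6-month median. If a share p is removed for progression before month 6, 6-month PFS in those kept is 0.50/(1-p): 51.0%, 52.6%, 55.6% and 58.8% for p = 2%, 5%, 10% and 15%. Under the exponential null the starters' median is 6 + t, with t = -6 ln(1-p)/ln 2; at 15%, t = 1.41 and the median is 7.4 months.

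**5. Error with no drug effect.** The plan names no test, so six were simulated: 35 starters, exponential null, 100,000 trials per row, events before t removed. The log-rank rejects when (O - E)/sqrt(E) < -1.645, with E = L0 x total time at risk from day 1.

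| Lost to progression | One-sample log-rank | Range over six tests |
|---|---|---|
| 0% | 4.0% | 3.1-5.6% |
| 2% | 5.1% | 3.9-7.0% |
| 5% | 7.3% | 5.7-9.8% |
| 10% | 13% | 11-17% |
| 15% | 22% | 19-28% |

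The other five are the log-hazard, cube-root, signed likelihood ratio, averaged-variance log-rank and chi-square tests. The log-rank passes 5% at about 2% lost; across tests the crossing lies between 0% and 4%. One patient of 41 is 2.4%. Starting from 41 enrolled gives 7-8%, 12-14% and 21-23% at 5%, 10% and 15%. Removing progressors at random from the first 13.5 weeks gives 5.0% at 2% and 20% at 15%. A Kaplan-Meier test of 6-month PFS against 50% gives 4.1%, 5.3%, 7.3%, 13.4% and 22.1%.

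**6. Toxicity losses.** If all losses are toxicity unrelated to PFS, log-rank error stays at 4%.

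**7. Corrected tests.** With time at risk and E counted only from first dose (weeks 7, 13.5 and 20), error is 3.9-4.0%. The ITT comparison of all 41 gives about 4%.

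**The case against.** **It is labelled secondary, and the ITT estimate keeps every early progressor.** True: the unselected median and CI will stand beside it, and they are sound. But the null, alternative, significance level and power in Section 9 all belong to the starters-only test.

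**The losses may be mostly toxicity.** Possible. The plan does not split its 15%, so the bias could be near zero or could reach the bottom row of the table.

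**The control may have been selected in the same way.** That would remove the bias. No such selection is described.

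**The exponential curve sits badly with the plan's own loss figure.** This is the strongest point. A 6-month exponential implies 17% with events by week 7 and 41% by week 20, against up to 15% expected for progression and toxicity together. If hazard is low before first dose and higher after, with the median still 6 months and 5-15% lost, the exponential log-rank gives 0-20% for starters, at or below about 5% in seven of nine cases. So the absolute error need not exceed 5%. Selection still raises it: the same test on ITT gives 0-3.5% (15% lost, week 7: 20% against 3.5%; week 13: 5.4% against 0.5%). With a reference curve of the right shape, starters give 7-22% and ITT 4%. In those cases a wrong reference curve offsets the selection; the selection has not become harmless.

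**Stronger readings that a reader might infer.**
- That error reaches 26-83%, by removing everyone with an event before first dose. This needs 17-41% lost, more than the plan expects.
- That 2% is a fixed threshold. It belongs to particular tests, and the plan names none.
- That correction must take power below 80% or requires more patients. This rests on an effect model that the plan does not state.

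**Conclusion.** The concern holds. As written, the starters-only comparison is biased towards benefit, and the direction needs only that some non-starters are lost to progression and that the control was not selected likewise. Starters' 6-month PFS rises to as much as 58.8% with no drug effect if the full 15% is progression. Under the plan's exponential null, log-rank error is about 5% at 2% lost and 22% at 15% (19-28% across the tests examined). These sizes depend on the unnamed test, the unknown progression share and the exponential curve; with a flat-then-steep curve the absolute error can stay at or below 5% while still exceeding that of ITT. A reader might infer that the primary result is compromised; it is not, because the ITT Kaplan-Meier median and CI include all enrolled patients.

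**What to change.** 1. In 9.3 and 9.4, choose one. (a) For the pembrolizumab-treated comparison, count time at risk and expected events only from first dose (delayed-entry one-sample log-rank; error about 4% under the exponential null). With a constant 6-month hazard it is conservative (0-2%) if the true hazard rises later; a control curve's hazard after the same point, where available, held about 4%. (b) Compare the ITT population with 6 months and describe this as a test of the whole strategy, not of pembrolizumab alone.
2. Name the test. State the source and time zero of the 6-month value, and whether those patients had to be progression-free at a later point. Neither option controls error if that value is wrong for these patients, and Section 1.1 itself cites a 14-month median for low-volume proton reirradiation. Say whether the 25-treatment rule in 9.3.2 applies here. It would be a further selection, could exclude 4.0 Gy courses (60/4 = 15 treatments), and at five treatments a week would move the earliest start to about week 9 (5 + 4).
3. Recompute power for the corrected test under a stated effect model and N: the Study Summary attaches 80% to 41 patients, 9.4 to 35.

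**Cost.** (a) needs SAP wording and a few lines of code; (b) changes analysis roles and needs an amendment. The subgroup result will look less favourable. Power depends on the effect model: about 83% for ITT with 41 if the 10-month hazard acts from day 1. If it begins only at first dose (week 20 to week 7), power is about 52-74% for delayed entry and 34-65% for ITT; the week-7 ends drop out if the 25-treatment rule applies. A later cutoff can offset this: at 12 months' follow-up the ranges are 69-84% and 51-78%. Section 8.1.5.5 already follows PFS for up to 5 years, so that delays the result without adding visits. Added enrolment is not part of this fix.

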3.1 General Design

This is a phase II, single arm, unblinded trial of about 12 months of consolidation Pembrolizumab after proton reirradiation with or without concurrent chemotherapy for isolated local and regional thoracic recurrences of NSCLC. Forty-one patients will be treated with re-irradiation with or without standard concurrent chemotherapy to all gross disease with proton beam therapy. The intended radiation dose should be at least 60 Gy of reirradiation in 1.8-2.0 Gy fractions with or without concurrent chemotherapy or in 4.0 Gy fractions without chemotherapy, at the provider's discretion. This corresponds to daily fractionated radiation over a period of approximately 3-8 weeks. Four to 12 weeks after completing reirradiation, patients will begin Pembrolizumab consolidation. Pembrolizumab will be given at a fixed dose of 200 mg intravenously approximately every 21 days for 17 cycles (about 12 months) if there is no evidence of progressive disease or intolerable side effects.

Subjects will be evaluated approximately 30 days prior to consolidation Pembrolizumab and every 12 weeks (1 day after until the day of the next infusion) while on Pembrolizumab with radiographic imaging to assess disease status. If new signs or symptoms of progression occur between scheduled scans, directed imaging will be obtained at the clinically appropriate time point to document disease status. Investigators will make all treatment-based decisions using RECIST 1.1. Adverse events will be monitored upon initiation of Pembrolizumab treatment and continue throughout the trial and graded in severity according to the National Cancer Institute (NCI) CTCAE version 5.0. For the

Phase II Pembrolizumab Reirradiation

Pembrolizumab phase, all treatment-related toxicities will be recorded.

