Treatment with Pembrolizumab will continue for 17 cycles (about 12 months) in the absence of (1) documented disease progression, (2) unacceptable adverse event(s), (3) intercurrent illness that prevents further administration of treatment, (4) investigator's decision to withdraw the subject, (5) subject withdrawal of consent, (6) pregnancy of the subject, (7) noncompliance with trial treatment or procedure requirements, (8) institution of alternative systemic treatment, or (9) other administrative reasons. After the end of treatment, each subject will be followed for a minimum of 30 days for adverse event monitoring (serious adverse events will be collected for up to 90 days after the end of treatment). Subjects will have post-treatment follow-up for disease status until one of the following events: (1) disease progression; (2) initiation of non-study cancer treatment; (3) withdrawal of study consent; (4) loss to follow-up or (5) death. In addition, survival status beyond the establishment of PD or initiation of subsequent therapies will be documented.

The primary objective of the trial includes determination of PFS per RECIST 1.1. Secondary objectives include OS and safety/toxicity determination as assessed by a variety of parameters of adverse events (AEs), including incidence and time to first Grade 3-5 AE. Pre-specified adverse events of clinical interest during the Pembrolizumab phase include the following events: 1) Grade \geq 3 diarrhea 2) Grade \geq 2 colitis, 3) Grade \geq 2 pneumonitis, 4) Grade \geq 3 hypo- or hyperthyroidism, 5) Grade \geq 2 hypophysitis, 6) Grade \geq 2 uveitis, and 7) Grade \geq 2 nephritis. Participation in this trial will encourage supplying tumor tissue from either a newly obtained formalin-fixed specimen (preferred) or an older formalin-fixed, paraffin-embedded specimen, from locations not radiated prior to biopsy. The specimen will be evaluated at a central laboratory facility for expression status of PD-L1 in a retrospective manner. Eligibility for the trial will not be dependent upon PD-L1 expression status, but the sponsor may amend the trial in the future if new data arise regarding the predictive value of PD-L1 expression. Any patient enrolled on the study prior to such an amendment, however, will remain on study.

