8.2 Assessing and Recording Adverse Events

An adverse event is defined as any untoward medical occurrence in a patient or clinical investigation subject administered a pharmaceutical product and which does not necessarily have to have a causal relationship with this treatment. An adverse event can therefore be any unfavorable and unintended sign (including an abnormal laboratory finding, for example), symptom, or disease temporally associated with the use of a medicinal product or protocol-specified procedure, whether or not considered related to the medicinal product or protocol-specified procedure. Any worsening (i.e., any clinically significant adverse change in frequency and/or intensity) of a preexisting condition that is temporally associated with the use of the Merck's product, is also an adverse event.

Merck product includes any pharmaceutical product, biological product, device, diagnostic agent or protocol-specified procedure, whether investigational (including placebo or active comparator medication) or marketed, manufactured by, licensed by, provided by or distributed by Merck for human use.

Phase II Pembrolizumab Reirradiation

Adverse events may occur during the course of the use of Merck product in clinical trials or within the follow-up period specified by the protocol, or prescribed in clinical practice, from overdose (whether accidental or intentional), from abuse and from withdrawal.

All adverse events will be recorded from beginning with cycle 1 of Pembrolizumab through 30 days following cessation of treatment and at each examination on the Adverse Event case report forms/worksheets. Laboratory AE's will also start being recorded beginning with cycle 1 of Pembrolizumab. The reporting timeframe for adverse events meeting any serious criteria is described in section 8.2.3.1.

Applicable reporting to DSMC will occur as follows:

On-Site subjects (this includes any subjects enrolled at other sites on an in-house study)

1. All grade 3 or higher events (AE or SAE) within five business days of knowledge.
2. All unexpected deaths within 24 hours of knowledge.
3. All others deaths within 30 days of knowledge. Deaths of subjects off-study for greater than 30 days from the last study treatment/intervention are not reportable with the following exceptions:

Study Exceptions the CTSRMC will not Approve:

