	
Rechallenge Was the subject re-exposed to the Merck product in this study? If yes, did the AE recur or worsen? If yes, this is a positive rechallenge. If no, this is a negative rechallenge. (Note: This criterion is not applicable if: (1) the initial AE resulted in death or permanent disability, or (2) the trial is a single-dose drug trial); or (3) Merck product(s) is/are used only one time). NOTE: IF A RECHALLENGE IS PLANNED FOR AN ADVERSE EVENT WHICH WAS SERIOUS AND WHICH MAY HAVE BEEN CAUSED BY THE MERCK PRODUCT, OR IF REEXPOSURE TO THE MERCK PRODUCT POSES ADDITIONAL POTENTIAL SIGNIFICANT RISK TO THE SUBJECT, THEN THE RECHALLENGE MUST BE APPROVED IN ADVANCE BY THE U.S. CLINICAL MONITOR AS PER DOSE MODIFICATION GUIDELINES IN THE PROTOCOL.
	
	
Consistency with Trial Treatment Profile Is the clinical/pathological presentation of the AE consistent with previous knowledge regarding the Merck product or drug class pharmacology or toxicology?
	

The assessment of relationship will be reported on the case report forms /worksheets by an investigator who is a qualified physician according to his/her best clinical judgment, including consideration of the above elements.
	
Record one of the following	Use the following scale of criteria as guidance (not all criteria must be present to be indicative of a Merck product relationship).
Yes, there is a reasonable possibility of Merck product relationship.	There is evidence of exposure to the Merck product. The temporal sequence of the AE onset relative to the administration of the Merck product is reasonable. The AE is more likely explained by the Merck product than by another cause.
No, there is not a reasonable possibility Merck product relationship	Subject did not receive the Merck product OR temporal sequence of the AE onset relative to administration of the Merck product is not reasonable OR there is another obvious cause of the AE. (Also entered for a subject with overdose without an associated AE.)

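### The planned pembrolizumab-phase toxicity report is limited to treatment-related events, although all adverse events are recorded and Section 3.1 names safety measures with no causality limit

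*Combined protocol and SAP*

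**What the plan says.** **Reporting.** Section 9.3.1 splits the output in two: "Toxicity will be reported separately for definitive therapy and Pembrolizumab". For the definitive phase, Sections 9.3.1 and 9.4 report "grade 3 or higher treatment-related toxicities or any grade of pneumonitis or esophagitis". For the pembrolizumab phase they say: "For the Pembrolizumab phase, we will report all treatment-related toxicities". The note under Table 6 repeats this. Section 9 plans no all-cause table for the pembrolizumab phase.

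**Collection.** Section 8.2 states: "All adverse events will be recorded from beginning with cycle 1 of Pembrolizumab through 30 days following cessation of treatment". Sections 8.1.2.1 and 8.1.5.6 likewise record events without a causality condition. Section 3.1 says that in the pembrolizumab phase "all treatment-related toxicities will be recorded".

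**Safety measures in the design section.** Section 3.1 describes the safety objective as resting on several adverse event parameters, "including incidence and time to first Grade 3-5 AE". It then lists pre-specified events of clinical interest for the pembrolizumab phase, among them pneumonitis of grade 2 or higher. Neither item is restricted to related events.

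**Causality.** Table 8 in Section 8.2.4 asks a yes/no question about the Merck product. One ground for answering no is that "there is another obvious cause of the AE".

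**The concern.** Sections 2 and 3.4 set out to describe the toxicity of pembrolizumab given after chemotherapy and proton reirradiation, so the object of interest is the sequence. Lung toxicity is where the two parts overlap: reirradiation ends 4 to 12 weeks before pembrolizumab starts (Sections 3.1 and 5.2), and Section 8.1.5.3 bars entry to the pembrolizumab phase only for symptomatic pneumonitis of grade 3 or higher. Lower-grade pneumonitis can therefore be present at cycle 1.

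With one unblinded arm there is no control rate against which individual attributions can be checked. If the only planned table for this phase passes through an attribution filter, its rates depend on those judgements, and the error runs one way: events are removed, never added. The definitive-phase rule gives pneumonitis and esophagitis fuller reporting than other events. The pembrolizumab-phase rule has no matching clause, although a second possible cause of pneumonitis has by then been added.

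**Working it through.** The plan states no figure on this point, so the check is mainly a comparison of texts.

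**Step 1. Recorded against reported.** Under Section 8.2, adverse events of any cause are recorded from cycle 1 until 30 days after treatment. Under Sections 9.3.1 and 9.4, the related subset is reported. An event recorded in this phase and judged unrelated to any study therapy has no place in the planned output.

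**Step 2. Named measures against planned analyses.**

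| Measure in Section 3.1 | Causality limit there | Analysis in Section 9 |
|---|---|---|
| Incidence of grade 3–5 events | None | None stated |
| Time to first grade 3–5 event | None | None stated |
| Pneumonitis of grade 2 or higher, pembrolizumab phase | None | None stated |

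A related-only table cannot supply these measures, because they need the unrelated events too. The list of events of clinical interest in Section 8.2.3.2 does not fill the gap, as it does not include pneumonitis.

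**Step 3. Can pneumonitis fall between the two tables?** Take a case with onset after cycle 1 that the investigator attributes to reirradiation. The outcome depends on two terms that the plan leaves undefined. The definitive-phase clause on pneumonitis is read here as covering any grade and any cause, because *treatment-related* qualifies only the grade 3 or higher part.

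| *Treatment-related* means | Phases split by | Pembrolizumab table | Definitive table |
|---|---|---|---|
| Related to pembrolizumab | Onset date | No | No |
| Related to pembrolizumab | Causal therapy | No | Yes |
| Related to any study therapy | Onset date | Yes | No |
| Related to any study therapy | Causal therapy | No | Yes |

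The case is lost in one of the four combinations. It is not excluded by the text: Table 8 is the only causality scale and refers to the Merck product alone, and no section assigns an event to a phase.

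**Step 4. Size per case.** Section 9.4 expects up to 15% of 41 patients not to start pembrolizumab: 41 × 0.85 = 34.85, which agrees with the stated figure of at least 35. If *u* patients with an event are left out, the reported rate falls by *u*/35.

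- One patient: 1/35 = 2.9 percentage points.
- If the denominator were all 41 enrolled patients: 1/41 = 2.4 percentage points.

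The documents give neither an expected pneumonitis rate nor the share that would be attributed to reirradiation, so *u* cannot be estimated from them.

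**The case against.** The strongest reply is that the plan need not lose anything important. Section 9 applies *treatment-related* to the definitive phase as well, before any pembrolizumab has been given, so there the term must cover reirradiation and chemotherapy. Section 9.3 describes the whole regimen as one treatment plan in stages. On that usage, radiation pneumonitis after cycle 1 is related and is tabulated. Section 3.1 already singles out pneumonitis of grade 2 or higher, and Section 8.2 sends every grade 3 or higher event to the data and safety monitoring committee whatever its cause. Toxicity is a descriptive secondary objective with no test or boundary attached, and the underlying records remain available.

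Much of this stands, and it rules out several stronger readings that a reader might infer:

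- *Radiation-attributed pneumonitis will drop out of both tables.* The text supports only that it may, on one combination of undefined terms.
- *Section 3.1 says that unrelated events are not recorded.* It says that all related ones are recorded and does not exclude others. The same section has adverse events monitored from the start of pembrolizumab. The wording needs to be reconciled with 8.2 but is not a flat contradiction.
- *Prior reirradiation automatically makes an event unrelated under Table 8.* The other cause must be obvious, the criteria are guidance, and the decision is left to the investigator's judgement. Where the cause is uncertain, it is not obvious.
- *The reported rate would fall by some particular amount.* No event counts are given from which to derive one.

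The reply does not remove the gap in Section 9. Committee reporting is not an analysis, and naming measures in Section 3.1 is not a plan to tabulate them. Events judged unrelated to all study therapy stay outside the planned report on every reading of the two terms.

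**Conclusion.** The point holds as a reporting gap of minor to moderate weight. For the pembrolizumab phase, Section 9 plans only related toxicities, although Section 8.2 collects all events and Section 3.1 names measures that need all of them. In an unblinded single-arm trial with two successive possible causes of lung toxicity, that filter can understate the toxicity of the sequence.

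The loss of pneumonitis from both tables is a possibility only. It requires that *treatment-related* mean related to pembrolizumab and that phases be split by onset date. The size is unknown beyond 2.9 percentage points per omitted patient, assuming 35 starters. Sample size, power and the progression-free survival analysis are not affected.

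**What to change.** In Sections 9.3.1 and 9.4, for the pembrolizumab phase and beside the treatment-related table, add:

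1. adverse events of any cause, by grade;
2. the Section 3.1 measures: incidence of and time to first grade 3–5 event, with its time origin stated, and the pre-specified events of clinical interest, including grade 2 or higher pneumonitis;
3. pneumonitis and esophagitis of any grade regardless of attribution, matching the definitive-phase rule.

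In the same sections, say which therapies *treatment-related* refers to. State whether an event belongs to a phase by onset date or by causal therapy, and how an event present at cycle 1 that later worsens is counted. Reword the recording sentence in Section 3.1 and the note under Table 6 so that they agree with Section 8.2.

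The cost is one or two more descriptive tables from data that Section 8.2 already requires. No new assessments are needed, and no clinical management rule changes.
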